Upon confirmation of eligibility, subjects will be given the option through a formal consenting process to participate in the substudy prior to randomization. Participation in the main study will not be affected if subjects choose to decline participation in the substudy; however, subjects withdrawn from the main study will be withdrawn from the substudy.

If subjects do not qualify for the main study following completion of both screening visits, subjects will be given the option to participate in an optional blood sampling visit.

Treatment assignment and randomization:

During the Baseline Visit randomization will be done. Subjects will be randomized 1:1 to receive eplerenone PO 50mg daily or identical placebo for 12 months. The randomization list, stratified by gender, statin use, and presence of plaque will be generated by the biostatistician and kept by the research pharmacy. Daily dosing starts at 50 mg for the first week to avoid hypotension and will be increased to 50 mg twice daily at the 1 week safety visit. The study will be double-blinded. All subjects will receive lifestyle modification as described below.

Prior to randomization in all cases, the subject's primary care physician will be consulted regarding the appropriateness of the protocol including the lifestyle modification program with the subject's permission. Subjects are not eligible if they do not meet all of the enrollment criteria.

In the event that a subject wishes to withdraw from the study, the subject will be asked to return all unused study medication.

V. Study Procedures

Data Collection

Screening Visit 1 (to determine eligibility):

We will obtain:

- 1) Informed consent, history and physical, urine pregnancy test for females.
- 2) Blood for Cr, K, ALT, CBC, HbA1c, and HIV viral load.

Screening Visit 2 (to determine eligibility): Subjects will present after a 12 hr fast. If eligible from Screening Visit 1, we will obtain:

- 1) Urine pregnancy test for females as appropriate.
- 2) Coronary CTA for coronary plaque assessment. (This will not be performed if the subject has a previous reaction or contraindication to iodine-containing contrast media).
- 3) CT Abdomen for single slice screening at L4 for VAT determination.

Optional Blood Sampling Visit (For those who do not qualify after both screening visits): Subjects will present after an overnight 12 hr fast.

- 1) Fasting blood for markers of heart disease and inflammation

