Statistical Consideration: Aim I: The primary endpoint is change in CFR assessed by cardiac PET or change in sMBF by cardiac MRI. Secondary endpoints will include the following: change in sICAM and sVCAM. Shapiro-Wilk test will be used to assess for normality of distribution, and variables that are not normally distributed will be appropriately transformed prior to inclusion in multivariable models. We will compare the change in CFR from months 0 to 12 between treatment groups (eplerenone vs. placebo) using student's t-test for variables that are normally distributed or Wilcoxon rank sum test for variables that are not normally distributed. We will also compare changes in sICAM and sVCAM over 12 months between treatment groups using similar statistical methods. In all Aims, for subjects who withdraw after 6 months, but before the final 12 month visit, we will obtain biomarkers and imaging similar to that scheduled for the final 12 month visit if the subject agrees to have end of study testing. The analysis will be intention to treat (ITT). In order to properly handle subjects with missing outcomes (those who withdrew before 12 months), we will apply longitudinal linear mixed effects model analysis with random subject level intercepts and time slopes by which the longitudinal treatment effect can be examined by testing the significance of

Mineralocorticoid Receptor Antagonism for Cardiovascular Health in HIV The MIRACLE HIV Study

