time x treatment interaction, which will provide unbiased effect estimate under missing at random condition, which will be carried out by using augmented data sets created by multiple imputation. A sensitivity analysis will be performed to include only those subjects who completed the study. Baseline variables will be compared between treatment groups, and any variable that is statistically different between groups will be controlled for using multivariable modeling. It may be that subjects with more significant RAAS activation and dysregulation in aldosterone at baseline) are more responsive to eplerenone. We will phenotype the RAAS in subjects at the low sodium visit and, guided by this data, may use aldosterone levels prior to intervention as an index of RAAS activation and a covariate in assessing treatment response, to determine if eplerenone is more effective in the subpopulation with greater baseline aldosterone dysregulation and RAAS activation. Covariates that will be considered for inclusion in modeling, include variables that differ at baseline and those variables that may affect vascular dysfunction, inflammation, fibrosis and plaque (age, race, gender, BP, tobacco/illicit drug use, family history of CVD, lipids, and glucose), HIV parameters (viral load, CD4, and duration of HIV and ART use) and compliance. This will permit us to assess relevant factors that may mediate the effect of eplerenone on CFR in HIV and interactions between HIV and traditional risk factors contributing to eplerenone effects. Moreover, we will compare changes in CFR and vascular biomarkers over 12 months using regression analysis. We will perform Pearson's correlation for variables that are normally distributed and Spearman's correlation for variables that are non-normally distributed. If we see significant changes in specific biomarkers that correlate with changes in CFR, then we will run those specific biomarkers from stored serum at earlier time points (e.g. 6 months) to see if early changes in biomarkers can predict changes in CFR, as well as predict response to MR blockade. **Biostatistician Role:** The biostatistician will monitor data collection, quality and completeness of the study throughout all years of the grant. The biostatistician will create the randomization plan, using a permuted block algorithm, stratified for gender, statin use, and presence of plaque and provide the list to the study pharmacist (investigators will remain blinded). Identical placebo will be provided by the pharmacy. **Sample Size Determination:** Preliminary data from HIV subjects presented in this grant demonstrate a CFR 1.74 ± 0.73 (mean \pm SD) using cardiac PET. Supportive data are also derived from a longitudinal study by our team using cardiac PET, showing mean \pm SD change of CFR in diabetics treated with spironolactone 0.33 ± 0.83 vs. placebo: 0.02 ± 1.03 over 6 months (mean SD=0.93).⁴⁰ Given these data, we considered the range 0.73 - 0.93 SD to accurately reflect the potential variability of change in CFR for the proposed study. Based on this data, we now provide a range of detectable differences using 85% power and a revised increased sample size of 80 subjects, with an attrition rate of 15%, leaving 68 evaluable subjects. Thus, even choosing a conservative SD of 0.93, the study will be well powered to detect a difference in mean change of CFR of at least 0.69. As our preliminary data, using PET, show that HIV patients have a mean CFR 1.7, an increase of CFR to 2.4 with eplerenone is a clinically relevant increase associated with decreased morbidity and mortality. For the sMBF and biomarkers, this study has 85% power at a two-sided 0.05 α level to show a change in the variable of at least 0.74 SD after treatment with eplerenone vs. placebo.

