Statistical algorithms as detailed in Aim I will be applied to these specific endpoints. Moreover, the relationship between baseline CFR and non-calcified plaque volume will be assessed. Lastly, we will also determine whether longitudinal changes in coronary plaque are associated with changes in biomarkers of inflammation and immune activation to understand the potential relationship of these inflammatory indices as markers of improved indices of the coronary vasculature in response to MR blockade in the HIV. **Sample Size Determination:** In our prior studies assessing plaque in HIV, the median [IQR] change of noncalcified plaque volume over 12 mos was $6.7[-6.5, 29.8]$ mm 3 .¹³ We assumed a conservative SD of 18mm 3 taking the mean of the IQR. This study enrolling 80 subjects with 68 evaluable subjects will attain 85% power at a two sided α of 0.05 to detect a difference in noncalcified plaque volume of 13.3mm 3 between eplerenone vs. placebo, a clinically relevant change. For biomarkers, this study has 85% power at a two-sided 0.05 α level to show a change of at least 0.74 SD after treatment with eplerenone vs. placebo.

Aim IV: For this aim, the endpoint is change in MCP-1 between the low sodium and liberal sodium diets. Secondary endpoints will include: change in hsCRP, pentraxin3, IL6, Lp-PLA $_2$, sCD14, sCD163. We will test the change in biomarkers between the RAAS activated (sodium restricted) and RAAS suppressed states (sodium loaded) using the paired Student's t-test for normally distributed variables or Wilcoxon signed-rank test for non-normally distributed variables. We will apply Pearson's correlation for variables that are normally distributed and Spearman's correlation for variables that are non-normally distributed to determine whether there is a significant correlation between aldosterone during the RAAS activated state and TBR. Covariates considered for inclusion in modeling include variables that may affect vascular dysfunction, inflammation, and plaque (age, race, sex, BP, tobacco/illicit drug use, family history of CVD, lipids, glucose), and HIV parameters (viral load, CD4, duration of HIV and ART use). This will permit us to assess relevant factors that may mediate the effect of aldosterone on inflammation in HIV and interactions between HIV and traditional risk factors contributing to inflammation. **Sample Size Determination:** Preliminary data in HIV presented in this

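### Aim III takes half the interquartile range as the SD of plaque change; its own quartiles imply about 27 mm³, not 18, so power at 13.3 mm³ is about 52%, not 85%

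*Combined protocol and SAP*

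**What the plan says.** The Aim III endpoint is the change in noncalcified plaque volume on coronary CTA. Its sample-size paragraph (section VI, Biostatistical Analysis) takes the variability from the investigators' earlier work: "the median [IQR] change of noncalcified plaque volume over 12 mos was $6.7[-6.5, 29.8]$ mm 3". The next sentence turns that into a standard deviation: "We assumed a conservative SD of 18mm 3 taking the mean of the IQR". The power claim follows: "This study enrolling 80 subjects with 68 evaluable subjects will attain 85% power at a two sided α of 0.05". The effect in question is put at 13.3 mm³ between the arms, and the plan describes it as clinically relevant.

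The 68 evaluable subjects come from the Aim I paragraph ("a revised increased sample size of 80 subjects, with an attrition rate of 15%, leaving 68 evaluable subjects"). Randomization is 1:1 (section IV). Aim III adopts the Aim I methods, which compare 12-month changes between arms by "student's t-test for variables that are normally distributed or Wilcoxon rank sum test for variables that are not normally distributed". No other source or reason for 18 mm³ is given.

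**The concern.** The quartiles of a distribution enclose half of it. One SD either side of a normal mean encloses about 68%. Half the interquartile width is therefore smaller than the SD, by about a third for a normal variable. Using it as the SD understates the variability and overstates the power. Calling the value conservative points the reader the wrong way.

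At stake is the stated 85% power for the endpoint of one of the three main-study aims, at a difference the plan itself calls clinically relevant. A reader who trusts that figure could take a null plaque result as good evidence against a 13.3 mm³ effect, when the trial had roughly an even chance of missing it.

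**Working it through.** **Inputs.** Quartiles -6.5 and 29.8 mm³, median 6.7 mm³, assumed SD 18 mm³, difference 13.3 mm³, 85% power and two-sided alpha 0.05 (Aim III paragraph). 80 × 0.85 = 68 evaluable (Aim I paragraph), so 34 per arm at 1:1.

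**Where 18 comes from.** Width = 29.8 - (-6.5) = 36.3. Half the width = 18.15, which rounds to 18. The midpoint of the quartiles is (-6.5 + 29.8)/2 = 11.65, so the phrase about the mean of the IQR must refer to the half-width.

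**Reproducing the plan.** Two-sample t-test with noncentral t, 66 degrees of freedom:

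- Standard error = 18 × √(2/34) = 18 × 0.2425 = 4.37.
- Noncentrality = 13.3/4.37 = 3.05, giving power of 85.1%.
- The effect detectable with 85% power at 34 per arm is 0.7375 SD, and 0.7375 × 18 = 13.28 mm³.

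Both agree with the plan, so the 18 mm³ is what produces the 85%. The normal approximation gives 86.1%.

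**Converting the quartiles properly.** For a normal variable each quartile lies 0.6745 SD from the mean, so SD = 36.3/(2 × 0.6745) = 36.3/1.349 = 26.9 mm³. The plan's value is 18/26.9 = 67% of that. As a check, a normal variable with SD 18 would have about 69% of its values within 18.15 of its mean. The quartiles enclose 50%.

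**Power with the converted SD.**

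- Noncentrality = 13.3/(26.9 × 0.2425) = 2.04, giving power of 51.9% (53.1% by the normal approximation).
- Detectable difference with 85% power = 0.7375 × 26.9 = 19.8 mm³.
- Keeping 85% power at 13.3 mm³ would take 75 evaluable per arm, 150 in all. At 15% attrition that is 150/0.85, or about 177 enrolled.

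**Sensitivity to shape.** The quartiles are not symmetric about the median: 6.7 - (-6.5) = 13.2 below and 29.8 - 6.7 = 23.1 above. Scaling each side separately by 0.6745 gives a range of SDs.

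| SD (mm³) | Basis | Power at 13.3 mm³ (t-test, 34 per arm) |
|---|---|---|
| 18 | plan (half-width) | 85% |
| 19.6 | lower side, 13.2/0.6745 | 79% |
| 25 | illustrative | 58% |
| 26.9 | full width/1.349 | 52% |
| 30 | illustrative | 44% |
| 34.2 | upper side, 23.1/0.6745 | 35% |

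For the plan's rank-sum alternative, a simulated 13.3 mm³ shift gave about 50% power for normal data with SD 26.9. For a shifted lognormal matched to all three quoted points (an assumed shape), the rank-sum test had about 63% and the t-test about 30%.

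**The case against.** The strongest reply is that 52% is itself too firm. It rests on normality, which the quoted quartiles contradict. For non-normal data the plan moves to the rank-sum test, whose power depends on the shape of the distribution. This stands: 52% is a normal-theory t-test figure and should be labelled as one. It does not rescue the claim, because every shape tried stays below 85%.

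A second point is that the earlier data may not carry over. The title of the cited trial restricts it to patients with subclinical atherosclerosis. Here plaque is a stratification factor and is not among the listed inclusion criteria, so the spread could differ in either direction. The plan also does not say whether the quartiles describe one arm or pooled arms. If they are pooled, a treatment difference would have widened them and the within-arm SD would be smaller. Against that, a small-sample correction (assuming 17 to 40 subjects) would raise the SD to about 28 to 29 mm³. These are reasons to use the observed within-arm SD. None of them supports half the interquartile range.

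A mixed model or covariate adjustment might reduce the residual variance, but the plan's calculation takes no credit for either.

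Finally, the error biases neither the estimate nor the test, and a null result can be judged from its confidence interval. Only Aim I is labelled primary, and the Aim I and Aim II calculations do not use this SD. All of this is true and limits the damage to Aim III, but the plan still states 85% power for that aim, and that is wrong.

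**Conclusion.** The concern holds. The 18 mm³ is half an interquartile range used as a standard deviation, and the stated 85% power follows directly from it. On the plan's own quartiles, and within the normal-theory t-test framework that reproduces its figure, the SD is about 27 mm³. Power at 13.3 mm³ is then about 52%, and 85% power is reached only at about 19.8 mm³.

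These figures assume 34 evaluable subjects per arm, two-sided alpha 0.05, a normal shape, and prior data that represent this trial. The exact power is uncertain because of the skew (35% to 79% from the one-sided readings). The direction is not: no reading of the quoted quartiles gives an SD as low as 18. The error is confined to the Aim III endpoint.

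**What to change.** Rewrite the Aim III sample-size paragraph:

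- Replace 18 mm³ with 26.9 mm³ and show the conversion (36.3/1.349). Better still, use the observed within-arm SD if the investigators can obtain it from the earlier data.
- Delete the description of the SD as conservative.
- State that 68 evaluable subjects give 85% power for a difference of about 20 mm³, or about 52% power for 13.3 mm³.
- Say that these are t-test figures under normality, and give the 35% to 79% range to reflect the skew.
- Say whether the quoted quartiles come from one arm or from pooled data.

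The cost is the wording of one paragraph and a less favourable stated power. Enrolment, procedures and the analysis do not change.

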Baseline Visit 2 (RAAS Characterization): After Baseline Visit 1, subjects will be placed on an isocaloric low sodium diet for 6 days prepared by the metabolic phenotyping core at the BWH Center for Clinical Investigation for assessment of RAAS activation. Subjects will be asked only to consume the prescribed diet, containing 10 ± 2 mEq Na⁺, 100 ± 2 mEq K⁺, and 1000 ± 50 mg Ca²⁺ per 24 hours.

- 1) 24 hr urine will begin on the morning of this visit for volume, Na, K, Cr, cortisol, and aldosterone excretion rate.
- 2) Urine pregnancy test for females as appropriate.
- 3) Urine Na and Cr (rescheduled if subject is not in sodium balance).
- 4) Interval history and physical, including orthostatics.
- 5) Subjects will begin fast and lie supine overnight.
- 6) Fasting blood for PRA, serum aldosterone, K. DNA collection for genetic testing is optional.
- 7) Resume ad lib diet and administer study medication (eplerenone vs. placebo) to be started on the following day.

Substudy Visit 1 (Optional): Subjects will present on a low carbohydrate diet, after an overnight 12 hr fast. We will obtain:

- 1) STAT serum pregnancy test for females as appropriate.
- 2) Cardiac ¹⁸F-FDG-PET/CT to assess arterial inflammation.

Randomization and Blinding: Subjects will be randomized 1:1 to receive eplerenone

**Mineralocorticoid Receptor Antagonism for Cardiovascular Health in HIV
The MIRACLE HIV Study**

50mg daily or identical placebo for 12 months. The randomization list, stratified by gender, statin use and presence of plaque will be generated by the biostatistician and kept by the research pharmacy. Daily dosing starts at 50 mg daily for the first week to avoid hypotension and will be increased to 50 mg twice daily at the 1 week safety visit. The study will be double-blinded. All subjects will receive lifestyle modification as described below.

Safety Visits (1 wk, 2 wk, 4 wk, 3 mo, 6 mo, 9 mo post baseline visits): Subjects will only present after an overnight 12 hr fast for the 6 month visit. All safety visits include:

- 1) Urine pregnancy test for females.
- 2) Interval history and physical, including vitals.
- 3) Blood for Cr, K. Blood for markers of heart disease and inflammation for the 6 month visit only.
- 4) Collection of used study drug and provision of new supply.

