
Aim II: For this aim, the endpoint is change in myocardial ECV assessed by myocardial T1 mapping on cardiac MRI. Secondary endpoints will include the following: change in plasma IL-6, MCP-1, sCD163, sCD14 and serum hsCRP, galectin-3, cardiotrophin 1, lipocalin, PINP, PIIINP, BNP. Statistical algorithms as detailed in Aim I will be applied to

Mineralocorticoid Receptor Antagonism for Cardiovascular Health in HIV The MIRACLE HIV Study

these specific endpoints. Similar to Aim I, changes in ECV and inflammatory/fibrosis biomarkers over 12 mos comparing eplerenone vs. placebo will be assessed using ITT and longitudinal linear effects modeling with imputation and sensitivity analyses. By regression techniques and covariate analyses, we will also assess whether improvements in ECV from MR blockade will relate to improvements in diastolic strain.

Sample Size Determination: Thiara et al. show mean \pm SD ECV 0.28 ± 0.04 vs. 0.26 ± 0.03 in HIV vs. non-HIV using cardiac MRI.³⁰ To estimate the SD of change in ECV, we assumed an intrasubject longitudinal correlation over time $r=0.7$ among the HIV group, which results in a conservative SD estimate of 0.03. Based on this SD, the proposed study, with a revised sample size of 80 subjects and therefore 68 evaluable subjects considering a 15% attrition rate, will attain 85% power at a two sided α of 0.05 to detect a difference of at least 0.02 in longitudinal means of ECV. Thus our study is well powered to find a significant difference between arms that is clinically relevant, as each 0.03 increase in ECV raises the risk for mortality or CV morbidity by 50%.²³ For biomarkers, we have 85% power at a two-sided 0.05 α level to show a change of at least 0.74 SD comparing eplerenone vs. placebo.

Aim III: For this aim, the endpoint is change in noncalcified plaque volume assessed by coronary CTA. Secondary endpoints will include: change in high risk plaque morphology (numbers of low attenuation and positively remodeled plaque) by coronary CTA.

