MIneralocorticoid Receptor Antagonism for CardiovascuLar hEalth in HIV The MIRACLE HIV Study

grant demonstrate a mean change in MCP-1 of 44.0 ± 41.8 pg/mL between a low sodium and ad lib sodium diet. Based on this SD, the proposed study, with a sample size of 42 subjects, and therefore 36 evaluable subjects considering a 15% attrition rate, will attain 85% power at a two sided α of 0.05 to detect a difference of at least 44.0 pg/mL in mean MCP-1 between the formally tested RAAS activated (sodium restricted) and RAAS suppressed (sodium loaded) states. For other biomarkers, we have 85% power at a two-sided 0.05 α level to show a change of at least 0.95 SD between RAAS activated and suppressed states.

Aim V: For this aim, the endpoint is change in TBR assessed by cardiac ^{18}F -FDG-PET/CT. Secondary endpoints include: change in hsCRP, pentraxin3, IL6, Lp-PLA2, MCP-1, sCD14, sCD163. Statistical algorithms as detailed in Aim I will be applied to these specific endpoints. Similar to Aim I, changes in TBR and inflammatory biomarkers over 12 mos comparing eplerenone vs. placebo will be assessed using ITT and longitudinal linear effects modeling with imputation and sensitivity analyses. We will also determine whether longitudinal changes in arterial inflammation are associated with changes in biomarkers of inflammation and immune activation to understand the potential relationship of these inflammatory indices as markers of improved indices of the coronary vasculature in response to MR blockade in the HIV. **Sample Size**

Determination: In our prior studies assessing arterial inflammation on ^{18}F -FDG PET, the mean \pm SD (95% CI) TBR at baseline among HIV subjects was 2.23 ± 0.45 (2.07, 2.40)mm 3 .⁷⁴ In order to estimate the SD of change in TBR, we assumed the intrasubject longitudinal correlation over time $r=0.75$, which results in a conservative SD estimate of 0.34. This study enrolling 42 subjects with 36 evaluable subjects will attain 85% power at a two sided α of 0.05 to detect a difference in mean TBR changes of 0.32 between eplerenone vs. placebo, a clinically relevant difference in the changes as our preliminary data show that non-HIV subjects have a mean TBR 1.89. For biomarkers, this study has 85% power at a two-sided 0.05 α level to show a mean change of at least 0.95 SD after treatment with eplerenone vs. placebo.

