
**Mineralocorticoid Receptor Antagonism for Cardiovascular Health in HIV
The MIRACLE HIV Study**

Optional Substudy--Cardiac 2-deoxy-2-18F-Fluorodeoxyglucose Positron Emission Tomography/Computed Tomography (18F-FDG-PET/CT) and Radiation:

The two cardiac PET/CT scans will involve exposure to radiation for research purposes. Subjects will receive a scan before and after a mineralocorticoid receptor antagonist. For ¹⁸F-FDG-PET/CT, the administered dose from ¹⁸F-FDG for a typical cardiac study is 370 MBq (10 mCi=7.03 mSv) and the effective dose for an attenuation correction scan of head/neck/upper abdomen is about 1.58 mSv. The total effective dose from two FDG-PET/CT studies would be 17.22 mSv. This is equivalent to the amount of radiation an individual would normally get in 5 years and 7 months from natural background sources from the earth and the sky. A STAT serum pregnancy test will be performed on the day of prior to commencement of the study. In addition, there may be incidental findings on the PET study. If any of these findings are clinically significant, subjects will be informed, referred to their primary care physician for further evaluation, and withdrawn as appropriate from the study.

Optional Substudy--Radiation Exposure The total estimated radiation exposure for the entire study (main study+substudy) would be 32.49 mSv. This is equivalent to the amount of radiation an individual would normally get in 10 years and 6 months from natural background sources from the earth and the sky. (See also sections radiation exposure for other precautions and cardiac ¹⁸F-FDG-PET/CT above for specific radiation exposure related to the substudy.)

Optional Substudy--Blood draw The total amount of blood drawn for the substudy will be approximately 4 mL over 1 year for females only. This will be a minimal amount added to the main study. The total blood drawn for subjects completing the entire study (main study+substudy) is equivalent to approximately 564ml (over a period of 12 months).

Optional Blood Sampling Visit (for those that do not qualify after completion of both screening visits)--Blood draw The total amount of blood drawn for the Optional Blood Sampling Visit will be approximately 48 ml. This will be a minimal amount added to the screening visits. The total blood drawn for subjects completing this optional visit (screening visits+optional visit) is equivalent to approximately 73 ml.

VIII. Potential Benefits

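### Five inflammatory markers are tested by treatment arm twice, in all randomised subjects (Aim II) and again in the optional substudy (Aim V), with no rule for which result governs

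*Combined protocol and SAP*

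**What the plan says.** Section VI, Aim II gives as secondary endpoints "change in plasma IL-6, MCP-1, sCD163, sCD14 and serum hsCRP, galectin-3, cardiotrophin 1, lipocalin, PINP, PIIINP, BNP". These are compared between eplerenone and placebo over 12 months by the Aim I methods, "with a revised sample size of 80 subjects and therefore 68 evaluable subjects considering a 15% attrition rate". The stated biomarker sensitivity is 0.74 SD at 85% power, two-sided 0.05.

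Aims IV and V stand under the optional substudy in section II. For Aim V, section VI says: "Secondary endpoints include: change in hsCRP, pentraxin3, IL6, Lp-PLA2, MCP-1, sCD14, sCD163". The arms, the 12-month interval and the statistical methods are those of Aim II. The size differs: "This study enrolling 42 subjects with 36 evaluable subjects will attain 85% power", and for biomarkers "85% power at a two-sided 0.05 α level to show a mean change of at least 0.95 SD". Aim IV, a paired comparison of two sodium states, uses the same 36 evaluable subjects and the same 0.95 SD for its other biomarkers.

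On where the blood comes from:

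- Section V, Bionutrition Visit, draws CRP, IL-6, MCP-1, sCD14 and sCD163 in every main-study subject before Baseline Visit 1 and before the 12 Month Visit.
- The substudy visits list a serum pregnancy test and the FDG-PET/CT scan. Section VII states: "The total amount of blood drawn for the substudy will be approximately 4 mL over 1 year for females only".

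Nothing in section VI says whether the Aim II or the Aim V result is the trial's answer for a marker named in both.

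**The concern.** Aims II(b) and V(b) ask the same question of these five markers: does eplerenone change them over 12 months relative to placebo? The plan answers it twice, the second time in about half of the same people and from the same blood. Two p-values per marker result, with no order of precedence. A report could then cite whichever is significant, or could present a non-significant substudy result as evidence against an effect that the larger analysis shows. Participation in the substudy is by optional consent and is not a stratification factor, so the smaller comparison has no design advantage to offset its size.

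**Working it through.** **Inputs.** Two-sided alpha 0.05, 85% power and 1:1 allocation (sections IV and VI). Aim II: 80 × 0.85 = 68 evaluable, 34 per arm. Substudy: 42 × 0.85 = 35.7, stated as 36, so 18 per arm if the arms are equal. The calculation treats each comparison as a two-sample t-test on change, the plan's basic test.

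**Overlap.** Aim V lists seven markers. Five are also in Aim II; pentraxin-3 and Lp-PLA2 are not.

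**Formula.** With n per arm and true difference d in SD units, the t statistic has 2n − 2 degrees of freedom and noncentrality d√(n/2). The normal approximation to the detectable difference is (1.960 + 1.036) × √(2/n).

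| Evaluable (per arm) | 85% detectable, normal | 85% detectable, t | Power at 0.74 SD (t) | Power at 0.95 SD (t) |
|---|---|---|---|---|
| 68 (34) | 0.727 SD | 0.738 SD | 85.2% | 97.1% |
| 42 (21) | 0.925 SD | 0.948 SD | 64.8% | 85.2% |
| 36 (18) | 0.999 SD | 1.028 SD | 57.8% | 79.1% |

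For example, at 0.74 SD with 18 per arm the noncentrality is 0.74 × √9 = 2.22 on 34 degrees of freedom, giving 57.8%.

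- The Aim II figure of 0.74 SD is reproduced on 68 evaluable subjects.
- The Aim V figure of 0.95 SD is not reproduced on 36. It matches all 42 enrolled with no attrition.

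**Testing twice.** A subset of 36 (18 per arm) nested at random in 68 was simulated with normal data and 40,000 replicates:

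| True difference | Only the full set significant | Only the subset significant | At least one significant |
|---|---|---|---|
| 0 | 3.3% | 3.1% | 8.2% |
| 0.74 SD | 29.3% | 1.5% | 86.9% |

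Adding the substudy test at 0.74 SD raises the chance of a significant result from 85.4% (full set alone, same simulation) to 86.9%. Under no effect it raises it from 5% to 8.2%.

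Over five independent markers, the chance of at least one false positive goes from 1 − 0.95⁵ = 23% to 1 − 0.918⁵ = 35%. Independence is unlikely for inflammatory markers. With an assumed pairwise correlation of 0.5, simulation gives 18% and 29%.

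**Aim IV.** A paired t-test on n subjects has noncentrality d√n on n − 1 degrees of freedom. With n = 36, 85% power is reached at 0.51 SD, which for MCP-1 is 0.514 × 41.8 = 21.5 pg/mL. The planned 44.0 pg/mL is 44.0/41.8 = 1.05 SD, with power above 99.9%. The stated 0.95 SD equals Aim V's two-sample figure; it does not describe a paired test on 36.

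**The case against.** The strongest reply is that the trial loses no power on these five markers. Aim II tests them in 68 evaluable subjects with the power the plan claims, and that is correct. A reader might infer from the 36-subject sizing that the plan gives up power to detect an anti-inflammatory effect. For these markers the documents do not support that; Aim V(b) is a weaker repeat of an adequate analysis.

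Second, a reader might say that the two tests contradict each other in about 31% of trials at 0.74 SD. About 29 of those 31 points are the smaller test missing an effect that the larger one finds, as a half-size sample often will. The error concern is the null case, 8.2% against 5%.

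Third, a reader might infer that pentraxin-3, Lp-PLA2 and the Aim IV(a) diet comparison could simply be run in everyone. The sodium visits are indeed main-study visits: "After Baseline Visit 1, subjects will be placed on an isocaloric low sodium diet for 6 days". However, no listed draw names pentraxin-3 or Lp-PLA2. Baseline Visits 1 and 2 list only PRA, aldosterone and potassium as fasting blood, and the inflammatory panel is drawn on an ad lib diet at the Bionutrition Visit. Stored serum is mentioned only for possible re-assay at earlier time points. Suitable samples may exist, but the plan does not show it. Nor is Aim IV(a) tested twice by arm or underpowered: it is a paired comparison of diets at baseline, with ample power for its planned effect.

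Fourth, Aim V(c) relates change in TBR to change in markers, so marker values are needed in the substudy. This stands, and it is a reason to keep the values there, not a second by-arm test.

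Finally, these are secondary endpoints and both analyses are prespecified. That limits the harm but does not say which result governs.

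**Conclusion.** The concern holds for the five shared markers. They are by-arm 12-month endpoints in both Aim II and Aim V, on the same main-study blood, with no precedence rule. The substudy test has about 58% power at 0.74 SD against 85% for Aim II, and raises the per-marker chance of a significant result under no effect from 5% to about 8.2%. These figures assume equal arms, roughly normal changes and, for the 8.2%, that the substudy behaves as a random subset. The mixed-model and imputation analyses would shift them somewhat, but not the ordering.

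That both aims use the same blood is an inference: the substudy lists no biomarker draw, and its stated volume leaves no room for one.

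The stated 0.95 SD at 85% power is not delivered by 18 per arm, which gives about 79%, and it is the wrong figure for the paired Aim IV comparison. The matter concerns secondary endpoints and should be corrected; it does not threaten the trial's primary conclusions.

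**What to change.** 1. State in section VI that the treatment effect on hsCRP, IL-6, MCP-1, sCD14 and sCD163 is tested once, in all randomised subjects, under Aim II.
2. Remove these five from the by-arm secondary endpoints of Aim V, and have Aim V(b) cite the Aim II result.
3. Use substudy values of these markers only for the association between TBR change and marker change, Aim V(c).
4. Where substudy biomarker power statements remain, restate them. For pentraxin-3 and Lp-PLA2 by arm, 36 evaluable subjects give 85% power at about 1.03 SD. For the paired Aim IV markers, 36 subjects give 85% power at about 0.51 SD.
5. Name in the visit schedule the draws that supply pentraxin-3, Lp-PLA2 and the Aim IV markers at the two sodium states.

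The cost is wording only: no visits, and no assays beyond those already planned. The five shared markers lose nothing, since Aim II already has them in everyone.

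Extending pentraxin-3, Lp-PLA2 and Aim IV(a) to all subjects is optional. It would move the 85% detectable effect from 1.03 to 0.74 SD by arm, and from 0.51 to 0.37 SD paired, taking 68 evaluable. It depends on suitable stored samples and means assays in more subjects (80 − 42 = 38). The repair does not need it.
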